8.7.1.4 Expected Adverse Events

Expected Conduct-Related AEs

AEs are determined by the investigator. If in the investigator's opinion/experience an event is expected and not uncommon for that surgery (i.e., nausea in the recovery room), and it is not deemed different in severity from other episodes observed in the same situation, then it is up to the investigator's discretion to determine the event to be adverse.

An example of an expected conduct-related event: The use of an intravenous blood collection and indwelling venous cannula for the purpose of blood sampling and administration of investigational product may be accompanied by mild bruising and also, in rare cases, by transient inflammation of the vessel wall. After initial irritation, the presence of an indwelling cannula is usually painless and hardly noticeable. The same applies to single vein punctures for blood sampling.

Expected Adverse Drug Reactions

The definition below follows ICH-GCP (see also ICH Guideline for Clinical Safety Data Management: Definitions and Standards for Expedited Reporting):

Adverse Drug Reaction (ADR): In the pre-approval clinical experience with a new medicinal product or its new usages, particularly as the therapeutic dose(s) may not be established, all noxious and unintended responses to a medicinal product related to any dose should be considered as ADR. The phrase 'responses to a medicinal product' means that a causal relationship between a medicinal product and an AE is at least a reasonable possibility (definitely, probably, possibly), i.e., the relationship cannot be ruled out.

Investigational Product-Related Risks

In all completed clinical trials of Lymphoseek, involving 553 subjects, only 3 events (breast pain and injection site pain reported by subjects with breast cancer and injection site irritation reported by a subject with head and neck squamous cell cancer) were deemed definitely related to the administration of Lymphoseek by the investigator. The most common adverse reactions (incidence <1%) are injection site irritation and/or pain.

Adverse events from the radioactive dose are not expected, since the applied radiation doses are far below doses that can cause acute effects in human tissues.

Precautionary Measures

Special precautionary measures are not considered to be necessary for this study. In case of emergency, standard emergency procedures will be employed.

Unexpected Adverse Drug Reactions

An unexpected adverse drug reaction is defined as an adverse reaction that in nature and severity is not consistent with the applicable product information (e.g., Investigator's Brochure).

Any adverse experience that is not listed in the current Investigator's Brochure or which is, with regard to the specificity or severity, not consistent with the risk information shall be regarded as unexpected.

Examples would be (a) acute renal failure listed in the Investigator's Brochure with a subsequent new report of interstitial nephritis and (b) hepatitis with a first report of fulminant hepatitis. "Unexpected" as used in this definition refers to an adverse drug experience that has not been previously observed and included in the product information, rather than from the perspective of such experience not being anticipated from the pharmacological properties of the investigational product.

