3 OVERVIEW OF METHODOLOGY AND DESIGN

3.1 Overall Study Design

This is a prospective, open label, non-randomized, multicenter, blinded pathology assessment study to evaluate the tolerability and the diagnostic utility of Lymphoseek in pediatric subjects from neonatal to less than 18 years of age with melanoma, rhabdomyosarcoma, or other solid tumors where ILM and SLNB is appropriate and tumor resection or biopsy is planned. In accordance with local site practice, subjects may also receive Lymphazurin for a within-subject comparison of lymph node mapping.

The proposed study includes 3 visits: A screening visit for initial determination of eligibility and evaluation of clinical status, a baseline visit on the day of surgery, and a 4-to 14-day safety (in person) follow-up to assess subject disease management.

The Schedule of Study Events (see Appendix 1) contains a list of all study procedures and time points. Study activities are described in detail in Section 7.

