8.7 Safety

8.7.1 Adverse Events

8.7.1.1 Definition of Adverse Event

The definitions below follow International Conference on Harmonization (ICH) – Good Clinical Practice (GCP) (see also ICH Guideline for Clinical Safety Data Management: Definitions and Standards for Expedited Reporting).

Adverse Event (AE)

An AE is defined as any untoward medical occurrence in a subject administered a pharmaceutical product and which does not necessarily have a causal relationship with this treatment. An AE can therefore be any unfavorable and unintended sign (including an abnormal laboratory finding), symptom, or disease temporally associated with the use of a medicinal (investigational) product, whether or not considered related to the medicinal (investigational) product.

By definition for this study, all untoward medical occurrences beginning on the day of injection through the 4- to 14-day follow-up assessment are to be reported as AEs. Additionally, untoward medical events occurring prior to the day of injection will only be captured as AEs if they are related to a study procedure. SAEs will be reported from the time of consent through the end of participation. All adverse events should be followed until resolution or stabilization as determined by the investigator.

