8.7.1.5 Serious Adverse Events

Definition of Serious Adverse Events

Definition

The following SAE definition is based on ICH guidelines and the final rule issued by the Food and Drug Administration (FDA) and effective 06 Apr 1998. It is to be applied to AEs (defined in Section 8.7.1.1).

An SAE is classified as any untoward medical occurrence that at any dose:

- results in death, or
- is life threatening, or
- requires inpatient hospitalization or prolongation of existing hospitalization, or
- results in persistent or significant disability/incapacity, or
- is a congenital anomaly/birth defect, or
- is an important medical event (see paragraphs below).

The term 'life threatening' in the definition refers to an event in which the subject was at risk of death at the time of the event; it does not refer to an event that hypothetically might have caused death if it were more severe.

Medical and scientific judgment should be exercised in deciding whether it is appropriate to report an AE as serious also in other situations, such as important medical events that may not be immediately life threatening or result in death or hospitalization but may jeopardize the subject or may require intervention to prevent one of the other outcomes listed in the definition above. These should also usually be considered serious. Examples of such events are intensive treatment in an emergency room or at home for allergic bronchospasm or blood dyscrasias or convulsions that do not result in subject hospitalization.

Hospitalizations or other acute events that fall within the definition of SAE for planned elective surgeries, surgeries anticipated as part of the subject's primary surgical intervention such as reconstruction or plastic surgeries or resulting from extended surgical requirements that are secondary to intraoperative findings unknown at the initiation of surgery will not be considered serious adverse events.

Actions and reporting obligations in case of serious adverse events

The investigator should take appropriate diagnostic and therapeutic measures to minimize the risk to the subject.

If any SAE occurs over the course of the study, investigators or other site personnel will inform the Cardinal Health Drug Safety Group via phone immediately at [contact]. Written notification of the SAE will be faxed within one day (i.e., within 24 hours) of

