8.7.2.2 Vital Signs

Vital signs comprise the measurement of systolic and diastolic blood pressure, body temperature, respiration, and heart rate. All vital signs will be measured after the subject should be resting quietly for 1 minute. Heart rate should be measured immediately before or immediately after blood pressure measurement.

Vital signs will be measured at screening, baseline (before investigational product injection), 10, 30, 60 minutes post injection (Day 1), and at the 4- to 14-day follow-up visit.

Any clinically significant change from baseline that results in a change in subject management will be considered an AE.

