9.4 Safety Variables

9.4.1 Primary Safety Variable

The primary safety variable is the incidence of adverse events.

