9.9.3 Analysis of Primary Safety Variables

All AEs will be observed for each subject from enrollment until termination from the study. Prior to analysis, all AEs will be coded using MedDRA. Based on these coded terms, AEs will be summarized using system organ class and preferred term by tumor type and overall for all subjects in the safety population. AEs will also be summarized by severity, relationship to investigational product, and relationship to study procedure. All AEs will be listed.

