Appendix 1 Schedule of Events

Assessment	Screen (Day -29 to Day 0)	Pre- and Post-Injection Day 1 (hour: minute relative to Lymphoseek injection)							
		Before Injection	0:00	00:10	0:30	1:00	Surgery	After Surgery	days; in person)
Informed Consent	Х								
Entry Criteria	Х								
Medical History and Demography	Х								
Performance Status	Х								
Cancer Staging	Х								X
Vital Signs ^a	Х	Х		Х	Х	Х			Х
ECG	Х					Х			
Physical Examination	Х								Х
Review of Medications	Х							X	Х
Collect Blood and Urine for Central Lab ^b		X						Х	
Urine or Serum Pregnancy Test ^c		X							
Lymphoseek Administration			Х						
Lymphoscintigraphy SPECT/CT ^d			X						
Lymphazurin Administration ^e							Х		
Surgery and SLNB ^f							X		
Treatment Plan									X
Adverse Event Monitoring		Х	Х	X	X	X	X	X	X

^a Body weight and height will only be collected at screening

^b Blood and urine may be collected on Day 1 if performed before Lymphoseek injection

^c Pregnancy testing should be performed within 48 hours before Lymphoseek injection

^d Imaging may begin at the time of injection when performing dynamic imaging STATIC planar imaging should begin approximately 15 minutes post injection

e When used, vital blue dye will be administered at the start of or during surgery in accordance with the standard of care at the clinical site

f Surgery, node probing, and harvesting should occur between 15 minutes and 8 hours after Lymphoseek injection

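### Sections 8.7.1.1 and 8.7.1.4 differ on whether an expected surgical event must be recorded as an AE, and neither says which governs

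*Combined protocol and SAP*

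**What the plan says.** **Recording of AEs**

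- Section 8.7.1.1 gives the general rule: "all untoward medical occurrences beginning on the day of injection through the 4- to 14-day follow-up assessment are to be reported as AEs". Its AE definition covers any unfavorable, unintended symptom whatever the cause, and it states no exception for surgical events. Events before the injection day count only if related to a study procedure.
- Section 8.7.1.4 sets two conditions: the investigator regards the event as expected for that operation, and it is no different in severity from what is usually seen. Nausea in recovery is the example. If both hold, "then it is up to the investigator's discretion to determine the event to be adverse".
- Section 9.4.1: "The primary safety variable is the incidence of adverse events". Section 9.9.3 tabulates AEs by tumor type and overall, and by severity, relationship to investigational product and relationship to study procedure.
- Section 8.7.1.5 takes its AE definition for SAEs from 8.7.1.1, and excludes certain hospitalizations and acute events tied to the planned or extended surgery.
- Section 8.7.2.2, on vital signs: "Any clinically significant change from baseline that results in a change in subject management will be considered an AE". Sections 8.7.2.1, 8.7.2.3 and 8.8.2 have similar rules for physical examination, ECG and laboratory values.

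**Causality**

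- The only scale for the agents in 8.7.1.2, and its cut-off for calling an event related, are worded for the investigational product and/or Lymphazurin.
- Section 8.7.1.3 refers back to those definitions but asks for relationship to the investigational product, and 9.9.3 summarizes the same. Section 5.1 identifies that product as Lymphoseek.

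**The concern.** The same event is mandatory to record under one section and optional under another. Safety is the primary objective, the study has a single arm, and up to 10 centers contribute. If one center records routine post-operative symptoms and another does not, the reported incidence partly reflects site habit, and no control group would show it. An event that was never entered as an AE does not appear in the AE listing and is never rated for relationship to the study procedure, although 9.9.3 plans a summary of exactly that.

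The secondary issue affects only subjects given both agents. A reaction after the dye could be graded on the joint scale and then counted as related to the investigational product. Section 3.2 made the dye optional because of possible allergic reactions, so separating the two agents is of interest.

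**Working it through.** **1. Apply both rules to the plan's own example.** Take non-serious recovery-room nausea of usual severity on Day 1.
- Under 8.7.1.1 it is an untoward symptom inside the window, so it is reported.
- Under 8.7.1.4 both conditions hold, so the investigator may decide that it is not an AE.

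The two sections give different answers.

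**2. Look for text that settles it.**
- Section 8.7.1.3 has any AE recorded in source, but does not say whether this event is one.
- Section 9.9.3 says: "All AEs will be observed for each subject from enrollment until termination from the study". That applies to whatever has already been determined to be an AE, so it neither resolves the difference nor adds a second conflict.
- Section 8.7.1.5 points to 8.7.1.1 for the AE definition, but only for the purpose of SAEs.

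No section states precedence.

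**3. Who can be affected.** Appendix 1 states: "Surgery, node probing, and harvesting should occur between 15 minutes and 8 hours after Lymphoseek injection". Any subject who goes on to surgery can therefore have an event within the clause.

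**4. What limits the class.** Both conditions must be met. SAE criteria still apply, subject to the surgical exclusion in 8.7.1.5. Examination, vital-sign, ECG and laboratory findings that change management remain AEs. None of these requires a non-serious symptom such as nausea to be recorded.

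**5. Scale.** The plan states no target rate, precision or test for AE incidence, so there is no figure to reproduce. Inputs (Sections 8.1.1 and 9.7): 6 melanoma + 6 rhabdomyosarcoma + 15 other = 27 subjects. Let k be the number of subjects whose only AE is left out under the clause; the documents do not give k.
- Shift in overall incidence = k/27. For k = 0, 1, 2, 3 this is 0, 3.7, 7.4 and 11.1 percentage points.
- Shift per such subject within a tumor-type column: 1/6 = 16.7 points at the minimum of 6 (melanoma or rhabdomyosarcoma), and 1/15 = 6.7 points if all 15 others enroll.

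These are the steps of any proportion at these sample sizes. They are not evidence that a shift occurs.

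As an illustration under assumed rates, let p be the share of subjects with another AE, q the share with an expected surgical event (independent of the first), and s the share of those events recorded. Recorded incidence = 1 − (1 − p)(1 − q·s).
- p = 10%: incidence is 10% at s = 0. At s = 1 it is 1 − 0.9 × 0.9 = 19%, 1 − 0.9 × 0.7 = 37% and 1 − 0.9 × 0.5 = 55% for q = 10, 30 and 50%.
- p = 30%: incidence is 30% at s = 0. At s = 1 it is 1 − 0.7 × 0.9 = 37%, 1 − 0.7 × 0.7 = 51% and 1 − 0.7 × 0.5 = 65%.

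**6. Causality.** Section 8.7.1.2 defines 'related' for either agent or both, while 8.7.1.3 and 9.9.3 use the result for one agent. Nothing requires separate ratings and nothing forbids them. Overall AE incidence is unaffected. The relationship summary is unaffected if no dye is given or if sites rate Lymphoseek alone.

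**The case against.** The best defense is that a specific clause qualifies a general one. 'Untoward' is a term of judgment, and 8.7.1.4 opens by leaving AE determination to the investigator. Other parts of the plan also treat routine perioperative matters lightly: anesthesia medications need not be captured (7.2.8, 8.1.5), and certain surgery-related events are not SAEs (8.7.1.5). This reading is plausible, but the text does not state it. Even as an exception, the clause gives no event list and no severity reference, only the investigator's opinion, so uneven recording between sites would remain.

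Section 10.2 has the monitor compare eCRF entries with source data and check that AEs were properly reported. Medication review may also leave a trace of treated events. These are partial safeguards: a monitor cannot enforce one rule where the protocol itself permits discretion.

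A reader might go further and infer that the safety result is biased by a known amount, or that serious events could go unrecorded. The documents support neither. The number of affected events is not given, and the SAE criteria stand apart from their stated surgical exclusion.

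On causality, the joint wording permits agent-specific rating, and the categories that mention other agents or therapies could cover the dye. A reader might infer that dye reactions will be charged to Lymphoseek. That is one possible reading only. The eCRF specification (10.1.1) or the separate SAP (9.9.4), whose texts are not in the document reviewed, may already separate the ratings.

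**Conclusion.** The main point holds with high confidence. For non-serious, expected surgical events of usual severity, the plan gives two recording rules and does not say which governs, so sites can record the same event differently in the primary safety variable. The consequence is limited to completeness and comparability of a descriptive incidence; no threshold or test depends on it. Its size is unknown. The step of 3.7 points per affected subject assumes a denominator of 27 and a subject with no other recorded AE; more subjects would make the step smaller. The sponsor should correct this, but it does not invalidate the design.

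The causality point is secondary, with medium confidence. It concerns only subjects given dye, and only if the eCRF or SAP does not already separate the two ratings.

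**What to change.** **1. One recording rule.** Reconcile 8.7.1.1 and 8.7.1.4 so that every site follows the same rule. The preferable form is to record all untoward occurrences in the window, as 8.7.1.1 says, and to flag expected surgical events so they can be shown separately.

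The flag needs a definition. Section 3.1 says Appendix 1 "contains a list of all study procedures and time points", and that schedule includes the surgery, so a reader might infer that the existing procedure-relationship item already covers the operation. But 8.7.1.2 does not say so, and inclusion criterion 2 requires resection or biopsy to be planned anyway. Amend 8.7.1.2 to state whether 'study procedure' includes the tumor operation, or add a separate category for events related to surgery. Either way, operation-related events should be distinguishable from those due to study-specific procedures, and the pre-injection rule in 8.7.1.1 should be left unchanged.

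Cost: a short amendment and more routine post-operative AE entries.

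**2. Separate causality ratings.** Rate causality for Lymphoseek and, where given, for Lymphazurin, and use only the Lymphoseek rating in the summary of relationship to investigational product.

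Cost: one extra eCRF item, relevant only to subjects given dye, and unnecessary if the eCRF or SAP already makes the distinction.

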8.7.1.5 Serious Adverse Events

Definition of Serious Adverse Events

Definition

The following SAE definition is based on ICH guidelines and the final rule issued by the Food and Drug Administration (FDA) and effective 06 Apr 1998. It is to be applied to AEs (defined in Section 8.7.1.1).

An SAE is classified as any untoward medical occurrence that at any dose:

- results in death, or
- is life threatening, or
- requires inpatient hospitalization or prolongation of existing hospitalization, or
- results in persistent or significant disability/incapacity, or
- is a congenital anomaly/birth defect, or
- is an important medical event (see paragraphs below).

The term 'life threatening' in the definition refers to an event in which the subject was at risk of death at the time of the event; it does not refer to an event that hypothetically might have caused death if it were more severe.

Medical and scientific judgment should be exercised in deciding whether it is appropriate to report an AE as serious also in other situations, such as important medical events that may not be immediately life threatening or result in death or hospitalization but may jeopardize the subject or may require intervention to prevent one of the other outcomes listed in the definition above. These should also usually be considered serious. Examples of such events are intensive treatment in an emergency room or at home for allergic bronchospasm or blood dyscrasias or convulsions that do not result in subject hospitalization.

Hospitalizations or other acute events that fall within the definition of SAE for planned elective surgeries, surgeries anticipated as part of the subject's primary surgical intervention such as reconstruction or plastic surgeries or resulting from extended surgical requirements that are secondary to intraoperative findings unknown at the initiation of surgery will not be considered serious adverse events.

Actions and reporting obligations in case of serious adverse events

The investigator should take appropriate diagnostic and therapeutic measures to minimize the risk to the subject.

If any SAE occurs over the course of the study, investigators or other site personnel will inform the Cardinal Health Drug Safety Group via phone immediately at [contact]. Written notification of the SAE will be faxed within one day (i.e., within 24 hours) of

becoming aware of the SAE to [contact] or emailed to [contact]. For fatal or life-threatening adverse events where important or relevant information is missing, active follow-up is undertaken immediately.

Pregnancy will have the same time reporting obligations to the sponsor as SAEs. Upon notification, Cardinal will provide a form for collection of pregnancy information.

All SAEs must also be recorded on the Adverse Event eCRFs.

Notification of the IRBs

The sponsor and/or the investigator will notify the IRBs about all relevant events (e.g., Serious Adverse Events [SAEs] and Suspected, Unexpected, Serious Adverse Reactions [SUSARs]) according to all applicable regulations.

Notification of the authorities

The sponsor will process and report all relevant events (e.g., SAEs, SUSARs) to the authorities according to all applicable regulations.

Sponsor's notification of the investigators

The sponsor will inform all investigators about reported relevant events (e.g., SAEs, SUSARs) according to all applicable regulations.

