7.2.7 Day 1: Imaging and Surgery

Dynamic and/or planar SPECT or SPECT/CT imaging may be performed prior to surgery as described in Section 8.3, and any finding will be documented and recorded on the appropriate CRF.

Vital signs and ECGs will be recorded as described in Section 7.2.6.

If Lymphazurin is to be used, it should be administered in the operating room at the start of or during surgery prior to transcutaneous surveying. The injection will be performed as deemed appropriate by the surgeon and in accordance with the standard of care at the clinical site. Fifteen minutes to 8 hours after Lymphoseek injection, subjects will undergo surgery to remove the primary tumor, ILM will be performed, and SLN(s) will be harvested. Locations of both hot and blue (when applicable) nodes will be recorded.

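### The surgical exemption in section 8.7.1.5 covers acute events as well as planned hospitalization, so an acute perioperative event can lose SAE status and expedited reporting

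*Combined protocol and SAP*

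**What the plan says.** Section 8.7.1.5 defines an SAE as an untoward occurrence meeting any one of six criteria: death, life threat ("is life threatening, or"), inpatient hospitalization or its prolongation, disability, congenital anomaly, or an important medical event. No criterion is limited by cause or setting.

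Later in the same section an exemption opens with "Hospitalizations or other acute events that fall within the definition of SAE for planned elective surgeries". It extends to surgery anticipated as part of the primary intervention and to events "resulting from extended surgical requirements that are secondary to intraoperative findings unknown at the initiation of surgery will not be considered serious adverse events".

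On timing, section 7.2.7 says: "Fifteen minutes to 8 hours after Lymphoseek injection, subjects will undergo surgery to remove the primary tumor". The same section places Lymphazurin, when used, in the operating room at the start of or during surgery.

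On what is counted, section 9.4.1 says: "The primary safety variable is the incidence of adverse events". Section 8.7.1.1 says that "all untoward medical occurrences beginning on the day of injection through the 4- to 14-day follow-up assessment are to be reported as AEs".

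**The concern.** An exemption for a planned hospital stay is normal, because every subject here is admitted for an operation and that admission is not an untoward event. This text goes further. It also exempts acute events, and it describes them as events that already meet the SAE definition. Nothing in the sentence holds back fatal or life-threatening events, or events related to the tracer or the dye.

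Safety and tolerability are the primary objective (section 2.1). Section 3.2 makes the dye optional because of possible allergic reactions in a vulnerable population. When the dye is used, that hazard arises in the operating room, in the setting to which the exemption is tied. What is at stake is whether such an event reaches the sponsor at once as an SAE or arrives later as an ordinary AE.

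**Working it through.** The plan states no figure that depends on this clause, so there is nothing to reproduce. The check follows one hypothetical case through the text: an acute life-threatening event during the operation.

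1. **Is it an AE?** Yes. Surgery takes place on the day of injection, inside the reporting window of section 8.7.1.1, and Appendix 1 schedules AE monitoring at surgery. Section 8.7.1.4 lets the investigator decide whether an event is adverse, but only if it is expected, not uncommon for that operation and no different in severity from the usual. A life-threatening reaction does not meet those conditions.

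2. **Is it an SAE?** Under the criteria, yes. Under the exemption, it "will not be considered serious adverse events" if the site regards it as an acute event of the planned, anticipated or extended surgery. Section 8.7.1.2 requires seriousness to be judged for every AE, but by the criteria of section 8.7.1.5, so it leads back to the same two paragraphs.

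3. **What depends on SAE status?** The immediate phone call and the written notice within 24 hours, both in section 8.7.1.5. Notification of IRBs, authorities and other investigators is illustrated there by SAEs and SUSARs. An event not classified as serious follows the ordinary route of section 10.1, which is eCRF entry as soon as possible with no fixed deadline.

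4. **What does not depend on it?**
   - The primary safety variable, which counts all AEs (section 9.4.1).
   - The tables by system organ class, severity and relationship, and the listing of all AEs (section 9.9.3). The severe grade in section 8.7.1.2 includes life-threatening events.
   - DSMC review, which covers all available safety information at the enrollment hold after the first three subjects (section 9.11) and safety listings and tables after that (section 9.10).

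   Section 9.9.3 names no summary by seriousness, so no specified table would change.

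5. **How often could the clause matter?** The documents give no rate. If each of 27 subjects (the planned minimum, section 8.1.1) independently had probability p of an acute perioperative event meeting an SAE criterion, the chance of at least one is 1 − (1 − p)^27. The values of p below are assumptions.

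| Assumed p | 1 − (1 − p)^27 |
|---|---|
| 1% | 1 − 0.99^27 = 24% |
| 2% | 1 − 0.98^27 = 42% |
| 5% | 1 − 0.95^27 = 75% |
| 10% | 1 − 0.90^27 = 94% |

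This is the chance that a site has to choose between the two paragraphs, not the chance that it chooses wrongly.

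**The case against.** The strongest reply is that the exemption is tied to surgery and can be read narrowly. A reaction to the tracer or dye is not an event for a planned operation and does not result from extended surgery. The paragraph just before it gives intensively treated allergic bronchospasm as an example of an event usually considered serious. An express exception to a general definition is also not in itself a contradiction. In addition, section 8.7.1.5 calls for immediate active follow-up of fatal or life-threatening adverse events when information is missing, in words not limited to SAEs, and commits the sponsor to regulatory reporting.

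Part of this stands. The narrow reading is possible and may be what was intended. But if only the operation and its hospital stay are exempt, the words *or other acute events* have almost nothing to do, and nothing in the sentence requires that reading. The bronchospasm example concerns treatment in an emergency room or at home, so it does not settle the operating-room case. The follow-up duty concerns missing information and does not replace the first report. With up to 10 sites, the same event could be classified in different ways.

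The objection is fully right about the analysis. A reader might infer that an exempted event drops out of the safety endpoint, the safety tables or DSMC review. The documents do not support that: the clause removes the label of seriousness and leaves the AE in place. A reader might also work out how one exempted event changes an SAE proportion among 27 subjects, but the plan specifies no such proportion. Nor do the documents say that surgery is when a drug reaction is most likely, and the dye argument applies only to subjects who receive it.

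**Conclusion.** The point holds as a defect in SAE classification and expedited reporting. The exemption conflicts with the unqualified criteria in its own section, and a site that follows its wording could treat a life-threatening or product-related perioperative event as non-serious. The consequence is a delayed or missing phone report, 24-hour notice and SAE/SUSAR handling.

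The effect on the planned statistical analysis is nil. The practical size cannot be estimated from the documents, because it depends on the event rate and on how each site reads the clause. The conclusion assumes only that some site adopts the broad reading, which the text permits. Because the trial's primary purpose is safety in children and the remedy is small, the wording should be changed.

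**What to change.** Reconcile the two paragraphs of section 8.7.1.5:

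- Limit the exemption to hospitalization, or prolongation of hospitalization, for the planned, anticipated or extended procedure itself.
- Delete *or other acute events*.
- State that an untoward event during or after surgery that meets any other SAE criterion remains an SAE.

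This amounts to rewriting one sentence and adding a short statement. No endpoint, analysis or sample size changes. The cost is a few more SAE reports of surgical complications.
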